Official Title: Does Endurance Improve with the use of Passy-Muir Valve for Patients with Tracheostomy?

Clinical Trial Number: NCT04941456

Study Closeout: June 24, 2024

STUDY PROTOCOL AND STATISTICAL ANALYSIS PLAN

Methods

Research design: Six period Quasi-Randomized Crossover Controlled Study. Enrollment will occur based off tracheostomy census report, site investigators will perform weekly pull of tracheostomy report to recruit appropriate patients.

Patient population: Patients approached to consent for enrollment in the study will be participants admitted to Gaylord Hospital with tracheostomy who are medically stable for ambulation with Physical Therapy and for the use of PMV valve. All patients over the age of 18 will be considered for the study.

Enrollment criteria:

1. **Inclusion criteria:**
 - a) Individual with tracheostomy who can tolerate daily 30 minute PT session with use of PMV and be able to maintain oxygen saturations above 88% with exertion.
 - b) Ability to understand and respond to simple verbal instructions and one step commands in English well enough to consent without any Gaylord interpretation.
 - c) Ability to ambulate a minimum of 10 feet with/without assistive device and with/without physical assistance.
2. **Exclusion Criteria**
 - a) Active seizures
 - b) Active Pregnancy
 - c) Uncontrolled hypertension
 - d) Cognitive deficits that would disrupt ability to provide informed consent
 - e) Enteric infection control precautions
 - f) Ongoing orthostasis
 - g) Actively on decannulation protocol
 - h) Medical instability that would cause a doctor to put therapy program on hold

Intervention: Standard intervention vs use of PMV to assess ambulation distance during 6MWT. The 6MWT will be performed each session to assess ambulation distance, alternating standard vs PMV intervention on sequential days to compare results. BORG Rating of Perceived Exertion (RPE) scale will be utilized pre and posttest daily to assess patient's subjective rating of physical exertion levels. Oxygen saturations and heart rate will be monitored pre and posttest via oximeter as well as during test if medically necessary.

Subject Assignment: Upon admission to Gaylord, appropriate patients are admitted under the inpatient program and tracked in the daily data pull of patient's with tracheostomy. Per hospital protocol, all patients will be evaluated by a physical therapist within the first 72 hours. If the patient meets criteria they will be asked to participate and then consented into the study by site investigators. Tracking forms will be compiled on inpatient therapy computers on research flash drive.

Study Timeline: Enrollment period will be 36 months and patients will receive two to six treatment sessions over a three week period. Treatment sessions will be scheduled in 30 minute increments to allot for testing time as well as collection of necessary data. Recruitment will remain open until we reach the goal of having 30 participants complete the full study. Partial data of early discharges, drop out due to changes in medical stability, or participants who are placed on

decannulation protocol during intervention period will still be included in the analysis. Data extraction will be retrieved from spreadsheets detailing results of 6MWT. Data will also be collected pre and post session on vital signs (HR and SaO₂) to monitor physiologic appropriateness of exercise response and patient's perceived rate of exertion via the BORG RPE scale.

Primary outcomes: The primary outcome we wish to assess is participant **endurance** with or without a PMV attached to their tracheostomy tube. This will be assessed using two measures, the standardized 6MWT, and the Borg-RPE scale. While the reliability and validity of the 6MWT in patients with a tracheostomy tube haven't been extensively reported, it has been shown to have good validity and reliability in cardiopulmonary patients, patients with a diagnosis of chronic obstructive pulmonary disease (COPD)^{1,2}, and survivors of acute respiratory distress syndrome.³ Further, the American Thoracic Society have made recommendations for use of the 6MWT as a pre- post-treatment comparison for several conditions, including pulmonary rehabilitation.⁴ As such, we feel that it is valid to use 6MWT duration and distance as objective measures of participant endurance when comparing PMV and open tracheostomy. The Borg-RPE scale is a standardized subjective measure of an individual's perceived exertion upon completing an activity. The validity and reliability of Borg-RPE has been extensively assessed, and has been recommended as a valid measure to track patient progress during rehabilitation.⁵⁻⁹ For this study, pre- and post-6MWT Borg-RPE assessments will be collected. Paper copies and notes of both assessments will be collected during the study session and then later transcribed into an electronic data collection sheet made in Microsoft Excel.

Secondary outcomes: Participant endurance and response to completing the 6MWT with or without a PMV will also be assessed through other metrics, including pre- and post-6MWT heart rate; pre- and post-6MWT oxygen saturation; post-6MWT supplemental oxygen requirements; and 6MWT assistive device usage. In addition to being physiological indicators of participant exertion and endurance,^{10,11} several of these metrics have been found to positively correlate with the Borg-RPE scale.⁵⁻⁹ Notes of these metrics will be collected during the study session and then later transcribed into an electronic data collection sheet made in Microsoft Excel.

General characteristics: Demographic characteristics that will be collected will include participant age, sex, and race/ethnicity. Other general characteristics that will be collected will include, as applicable, participant length of stay, discharge location, admitting diagnosis or condition that lead to tracheostomy, time to decannulation attempt, and decannulation attempt outcome. To promote study transparency and reproducibility, this information will be used to provide a descriptive overview of the study population to provide context for any reported findings. These data will be collected through manual review of Gaylord Hospital's electronic medical record system; they will be transcribed directly into an electronic data collection sheet made in Microsoft Excel.

Statistical Analysis

Data Analysis: Data were analyzed using GraphPad Prism (version 10; GraphPad Software, Boston, MA) and RStudio (version 4.2.2, Posit Software, PBC, Boston, MA].

Descriptive data is reported as mean (standard deviation). If hypothesis testing was done, data were reported with a p-value, and significance was set at $\alpha=.05$. Data were determined to be missing completely at random and were dealt with via complete case analysis. Data were also assessed for violations in assumptions of their given tests, and were dealt with via non-parametric analysis as necessary.

Paired t-tests or Wilcoxon tests were utilized as necessary to evaluate between-group differences in continuous outcome variables.

References:

1. Six Minute Walk Test / 6 Minute Walk Test [Internet]. Physiopedia. [cited 2022 Aug 5]. Available from: https://www.physio-pedia.com/Six_Minute_Walk_Test/_/6_Minute_Walk_Test
2. 6 Minute Walk Test [Internet]. Shirley Ryan AbilityLab. [cited 2022 Aug 15]. Available from: <https://www.sralab.org/rehabilitation-measures/6-minute-walk-test>
4. ATS Statement: Guidelines for the Six-Minute Walk Test. *Am J Respir Crit Care Med* [Internet]. American Thoracic Society - AJRCCM; 2002 Jul [cited 2022 Aug 15];166(1):111–117. Available from: <https://www.atsjournals.org/doi/10.1164/ajrccm.166.1.at1102>

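### Conditions follow a predictable alternation with no stated starting rule or concealment, so session timing and order can bias the within-person contrast

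*Combined protocol and SAP*

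**What the plan says.** Under Methods, Research design, the trial is described as a "Six period Quasi-Randomized Crossover Controlled Study". Under Intervention, a six-minute walk test (6MWT) is done at each session, "alternating standard vs PMV intervention on sequential days to compare results". No other rule links conditions to sessions.

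Subject Assignment covers screening, evaluation, consent and tracking forms. It does not say which condition comes first, how that is decided, or whether the next condition is hidden from anyone. Blinding is not mentioned anywhere.

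On timing, Study Timeline says "patients will receive two to six treatment sessions over a three week period". It gives no session dates and names nobody responsible for scheduling or postponing. The target is 30 participants who complete the study, and partial data from those who stop early are kept.

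Under Data Analysis, "Paired t-tests or Wilcoxon tests were utilized as necessary to evaluate between-group differences in continuous outcome variables". No term for period, sequence or session number is described. The significance level is .05.

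**The concern.** In a crossover each participant is compared with themselves, so ordinary selection of patients into arms is not the problem. What pairing does not remove is a systematic difference between the days, or the positions in the series, at which the two conditions are tested.

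There are two routes:

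- **Timing.** If the next condition is known, the decision to go ahead or wait on a marginal day can depend on it, with no misconduct needed. If valve sessions are put off on poor days more often than standard sessions, the valve looks better; if the reverse, it looks worse. A session-number term does not capture day quality. Randomising only the first condition does not help either, because the later ones remain predictable.
- **Order.** If most participants start with the same condition, the other is tested later on average. Recovery or growing familiarity with the walk test is then credited to the later condition, and an unadjusted paired test cannot separate the two.

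**Working it through.** **Inputs.** From the documents: alternation (Intervention), two to six sessions in three weeks and 30 completers (Study Timeline), paired t-test or Wilcoxon at .05 (Data Analysis). Two-sided testing is assumed, since sidedness is not stated. The figure of 30 cannot be reproduced, because no effect size, SD or power is given. For scale, 30 pairs give 80% power for a difference of 0.53 SD of the within-person difference.

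**Predictability.** Under alternation, 5 of the 5 conditions after session 1 are known.

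**Room in the schedule.** Six sessions on consecutive days take 6 days; the window is 21 days. This suggests that gaps are expected, but it is an inference.

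**Order.** With six sessions, the first condition occupies positions 1, 3, 5 (mean 3) and the second 2, 4, 6 (mean 4), a gap of 1 session. The gap is also 1 for two or four sessions and 0 for three or five. If a share f starts with standard and everyone has an even number of sessions, the bias is (2f − 1) × trend per session:

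- f = 1: 1.0 × trend
- f = 0.75: 0.5 × trend
- f = 0.5: 0

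A systematic shift from any source, in SDs of the within-person difference, raises the false-positive rate at n = 30 from 5% to 8.3% (shift 0.1), 18.5% (0.2) or 35.5% (0.3).

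**Timing, upper-end model.** Assume that sessions of one condition are put off whenever the day is among the worst share q, and that the other condition's never are. Staff foresee the day's result perfectly, days are independent, and the effect does not vary between patients. The bias in day-to-day within-person SDs is φ(z_q)/(1 − q). At q = 10%, z = −1.28 and φ = 0.1755, so the bias is 0.1755/0.90 = 0.195. False-positive rates come from simulated trials of 30 participants with no true effect:

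| Share put off | Bias (SD) | One pair each | Three pairs each |
|---|---|---|---|
| 5% | 0.11 | 7% | 11% |
| 10% | 0.20 | 12% | 28% |
| 20% | 0.35 | 30% | 73% |

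**Timing, weaker assumptions.** If staff judgement correlates only 0.5 with the day's result (also an assumption), the bias halves. At q = 10% it is 0.10 SD, and the rates are about 7% and 10%. At q = 20% they are about 10% and 21%. In another model, a share of one condition's sessions is moved to the better of two days, giving a bias of share × 0.564 SD. At 10% the rates are 5.5% (one pair) and 6.5% (three pairs); at 25% they are 8.3% and 15%.

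**Does the remedy work?** If the decision to postpone is made before the condition can be known, both conditions lose the same days and the rate returns to 5%. With order randomised within successive pairs, the second session of each pair can still be deduced (3 of 6). In the upper-end model at q = 10%, the bias then falls from 0.195 to about 0.098 SD and the three-pair rate from 28% to about 10–11%. It is halved, not removed.

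**The case against.** The strongest reply is that the timing route is not in the text. A reader might infer that staff chose the day for each condition, or that the result is therefore biased. The documents support neither. They do not say who schedules or postpones, and they report no postponement linked to condition. The Intervention paragraph has the conditions alternate day after day, which read strictly limits the choice of day. Inclusion criterion (a) requires participants to tolerate a daily session with the valve while maintaining saturation, and exclusion criterion (h) refers to therapy holds without regard to condition. Both make one-sided postponement less likely, though neither rules it out. That staff knew the condition is also inferred from the absence of any blinding.

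The larger error rates also depend on fully one-sided postponement with perfect foresight, including foresight of measurement noise. They should be read as near the top of the range for each share put off.

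These objections limit the size and certainty of the point. They do not touch its base: the order is predictable, the starting condition is unstated, and the test has no period term. The order route needs no discretion by staff.

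**Conclusion.** The plan has a real but unquantified risk of bias. The documents establish fixed alternation under a quasi-randomized label, with no rule for the starting condition, no concealment and no adjustment for period. Freedom over session days is a reasonable inference, not a stated fact.

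The direction is unknown. The size depends on how often sessions were put off by condition, how well staff foresaw the day, and how unevenly starts were split, none of which is given. At 10% put off, the false-positive rate runs from near nominal (5.5% to 6.5% in the mildest model) to 12% and 28% in the upper-end model. The order bias is zero if starts were balanced and at most one session's worth of trend if they were not. This warrants correction or disclosure, but does not show that the reported contrast is wrong.

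**What to change.** **For a future study or protocol revision.**

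- Replace alternation with a computer-generated, concealed random order of conditions, opened only after fitness to test is confirmed that day.
- State that randomising within successive pairs leaves the second session of each pair deducible, so it roughly halves the timing bias. A free random order of three and three sessions is less predictable (a best guess is right 68% of the time over six sessions, against 75% within pairs). However, its first two sessions would match with probability 2/5 = 40%, leaving some two-session participants without a pair.
- Because neither order removes predictability, also set session dates in advance, or log every postponement with its assigned condition and reason.
- Specify an analysis with period and sequence terms.

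The cost is one random list or set of envelopes and one log column. The small downside is that a participant may have the same condition twice in a row.

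**For this study.** Closeout is dated June 24, 2024 and Data Analysis is written in the past tense, so allocation cannot be changed. Report the actual sequences, starting conditions and session dates. Report postponed or skipped sessions by condition where they were recorded; the documents do not say that they were. Add a period-adjusted sensitivity analysis beside the primary result. It addresses trend but not day quality, so the postponement counts are still needed. The cost is one table and one extra model.

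### Conditions alternate daily from an unstated start and are compared by a paired test with no session term, so with unbalanced starts session-to-session drift is counted as a valve effect

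*Combined protocol and SAP*

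**What the plan says.** - **Research design (Methods):** the study is a "Six period Quasi-Randomized Crossover Controlled Study". What is quasi-randomized, and by what rule, is not explained.
- **Intervention (Methods):** the 6MWT is done at every session, "alternating standard vs PMV intervention on sequential days to compare results". Which condition comes first is not stated.
- **Subject Assignment:** this covers screening and consent only: "If the patient meets criteria they will be asked to participate and then consented into the study by site investigators". It contains no rule for sequence or starting condition.
- **Study Timeline:** "patients will receive two to six treatment sessions over a three week period". The target is 30 completers, and partial data are also analysed, so session counts will differ between participants.
- **Primary outcomes:** endurance is the primary outcome. "This will be assessed using two measures, the standardized 6MWT, and the Borg-RPE scale".
- **Data Analysis:** "Paired t-tests or Wilcoxon tests were utilized as necessary to evaluate between-group differences in continuous outcome variables". There is no session, period or sequence term, and no rule for reducing up to six sessions to one pair per participant.
- **Title block:** "Study Closeout: June 24, 2024".

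**The concern.** Participants are inpatients having physical therapy who repeat the same walking test for up to three weeks. Recovery and practice could both move the distance from one session to the next. The Primary outcomes section itself describes both measures as suited to showing change during rehabilitation.

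If conditions strictly alternate and most participants begin on the same one, the other condition is systematically tested later. A paired test cannot separate that from the valve. If distance rises over time, the bias favours whichever condition comes second, so it can run for or against the valve. Borg-RPE rests on the same sessions and the same tests. As the documents stand, a reader cannot tell whether the primary contrast measures the valve or the order of testing.

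**Working it through.** **Inputs from the documents.** Strict alternation; 2 to 6 sessions; goal of 30 completers; alpha 0.05; paired t or Wilcoxon test. The goal of 30 cannot be reproduced, because no effect size, SD, correlation or power is given.

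**Assumptions, not in the documents.** Two-sided testing; sessions averaged by condition within participant; normal errors; the drift, SD and start-split values below. There is no true valve effect in any scenario.

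**1. Bias for one participant.** Let distance drift by d per session. The bias is d times the mean session position of the second condition minus that of the first.

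| Sessions | First condition, mean position | Second condition, mean position | Difference |
|---|---|---|---|
| 2 | 1 | 2 | 1 |
| 3 | 2 | 2 | 0 |
| 4 | 2 | 3 | 1 |
| 5 | 3 | 3 | 0 |
| 6 | 3 | 4 | 1 |

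Even counts carry exactly one session of drift. Complete series of 3 or 5 carry none if drift is linear and sessions are averaged by condition; this fails if adjacent sessions are paired instead.

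**2. Bias across participants.** If a share f starts on standard, the net bias for even counts is (2f − 1)d: 0 at f = 0.50, 0.20d at 0.60, 0.33d at 0.67 and d at 1.00.

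**3. Type I error of the paired t-test.** n = 30, even session counts, 20,000 simulated trials per cell, drift expressed as a fraction of the SD of the paired difference:

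| Start split | Drift 0.10 SD | Drift 0.25 SD | Drift 0.50 SD |
|---|---|---|---|
| 15/15 | 0.050 | 0.043 | 0.028 |
| 18/12 | 0.049 | 0.050 | 0.053 |
| 20/10 | 0.056 | 0.065 | 0.100 |
| 22/8 | 0.058 | 0.092 | 0.181 |
| 30/0 | 0.081 | 0.262 | 0.754 |

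With balanced starts there is no bias, and the test is conservative because drift inflates the SD of the differences. Adjusting for starting condition gave 0.047–0.053 at every split where both starts occur.

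**4. In metres: six sessions each, common start, d = 5 m.** SE = sqrt(2·SD²/3)/sqrt(30). At SD 30 this is 24.5/5.48 = 4.47 m, so the noncentrality is 5/4.47 = 1.12 on 29 df and the rejection rate is 19.1%. At SD 15, 50 and 80 m the rates are 58.0%, 9.9% and 6.9%. As a cross-check, 5/24.5 = 0.20 SD, and 19.1% lies between the 8.1% and 26.2% of the last row above.

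**5. Mixed session counts.** 18 participants with six sessions and 3 each with 2, 3, 4 and 5; 5,000 trials per cell. With a common start, 24 of 30 have even counts, so the mean bias is 24/30 × d = 4 m at d = 5 and 8 m at d = 10.

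| Session SD | Error, d = 5 m | Error, d = 10 m |
|---|---|---|
| 15 m | 30% | 81% |
| 30 m | 11% | 31% |
| 50 m | 7% | 13% |
| 80 m | 6% | 8% |

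By start split at SD 30 and d = 10 m: 30/0 31%, 27/3 21%, 24/6 13%, 20/10 6%, 15/15 4%.

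**6. Does a session term repair it?**

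- *Linear term, linear drift:* error is 4.3–5.5% in every cell of step 5.
- *Linear term, front-loaded gains* (mean 30·(1 − exp(−t)) m, t = sessions since the first, common start): about 3 m of bias remains, with error of 18%, 9% and 6% at SD 15, 30 and 50 m.
- *Session factor, common start:* the design has 36 columns (30 participants, 5 session contrasts, 1 condition) but rank 35. Condition is aliased with session, so the model cannot be fitted.
- *Variance cost of the linear term, common start:* the correlation r of condition with session number is 1.0, 0, 0.447, 0 and 0.293 for 2 to 6 sessions. The inflation 1/(1 − r²) is infinite, 1.00, 1.25, 1.00 and 1.094. Over the step 5 mix it is 1.078.

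**The case against.** The strongest reply is that bias needs both drift and unbalanced starts, and the documents establish neither. The quasi-randomized label suggests that some allocation rule existed. Daily alternation is itself protective, since it caps linear bias at one session of drift. The metre values are invented, 10 m per session means 50 m from the first to the sixth session, and entry requires only 10 feet of walking. The 58% and 81% figures need a common start and an SD of 15 m. No size is offered for Borg-RPE. The session mix has 30 participants with only 18 at six sessions, which is not clearly the planned sample of 30 completers.

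All of this stands as a limit on size. What is shown is a gap in the design description together with an analysis that does not protect against it; a biased result is not shown. The gap itself is not answered, because no section supplies a start rule or a session term.

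On the remedy, three objections have weight:

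- The near-nominal error of the linear term was obtained under linear drift. The front-loaded case shows what is left when that fails.
- Session number is not calendar time when sessions may be spread over three weeks.
- Changing the primary analysis after closeout is post hoc. This is tolerable because the form of the model follows from the start split and not from the outcomes, and because the paired result is still reported.

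**Conclusion.** The concern holds and should be fixed. That the start rule and session term are absent is certain from the text. The consequence is conditional: with an even number of sessions and unbalanced starts, the paired contrast contains up to one session of drift, in either direction.

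Material error inflation needs a near-uniform start, or drift that is large relative to the SD. Under a common start, the illustrated type I error runs from 6% to 81% depending on drift and SD. At 20/10 it is 6% in the mixed-session example (SD 30 m, drift 10 m), and 5.6–10% across the drift ratios in the even-count table. With balanced starts the mean bias is zero and the test is at worst somewhat conservative. These sizes rest on assumed drift, SD and start splits, and on averaging sessions by condition.

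**What to change.** 1. Report how the first condition was assigned and how many participants started on each.
2. Make the primary analysis of 6MWT distance, and likewise of Borg-RPE, a session-level mixed model with condition, session number and a random participant effect. Report PMV minus standard with a 95% CI.
3. Keep the paired test as a sensitivity analysis, state how sessions are reduced to pairs, and say openly that the model was adopted after closeout.
4. Choose the session term from the start split. If starts are all or nearly all the same, use a linear term and state that front-loaded gains leave some bias. Use a session factor only if both orders are well represented; at least a third of participants on each is a reasonable working threshold.
5. A balanced start list can help only a repeat of the study, given the stated closeout.

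**Cost.** One model on data already collected and one line on start order. Under a common start, the linear term raises the condition variance by about 9% for six-session and 25% for four-session participants, and by 8% overall in the mix above. Two-session participants then add almost nothing on the valve separate from drift. A session factor costs nothing at 15/15 and about 13% at 20/10. At 24/6 it costs about 60%, and at 27/3 the variance is multiplied by about 3.2. These last two depend on who is in the minority: re-runs gave ratios of 1.4 to 2.1 and 2.4 to 6.1.

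### The primary outcome, endurance, rests on two unranked measures tested at .05 with no deciding variable, testing order or multiplicity rule; if any significant result counts, the chance of a false difference is up to 9.75% for the two

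*Combined protocol and SAP*

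**What the plan says.** The title asks one question: "Does Endurance Improve with the use of Passy-Muir Valve for Patients with Tracheostomy". The Primary outcomes section makes endurance the single primary outcome and continues: "This will be assessed using two measures, the standardized 6MWT, and the Borg-RPE scale". Neither measure is ranked above the other.

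Each measure can yield more than one variable. For the walk test, the same section says "we feel that it is valid to use 6MWT duration and distance as objective measures of participant endurance when comparing PMV and open tracheostomy". For perceived exertion it says "For this study, pre- and post-6MWT Borg-RPE assessments will be collected", without saying whether the post-walk score or the change is to be compared.

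Two places lean one way. The Intervention paragraph says "The 6MWT will be performed each session to assess ambulation distance" and does not mention duration. The Primary outcomes section describes the Borg scale as a measure of "perceived exertion upon completing an activity", which points to the post-walk score. Neither statement names the variable that decides.

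The Data Analysis section sets significance at .05 wherever a hypothesis test was done, and applies paired t or Wilcoxon tests to continuous outcomes that it does not name. It gives no sidedness, lead variable, testing order, success rule or multiplicity adjustment.

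**The concern.** A yes-or-no question is put to two measures, and the plan does not say how their results combine. Three rules are possible, and each has a different error rate: either measure may decide, both must succeed, or each speaks only for itself. Under the first, the error attached to the overall answer is larger than that of a single test.

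The two measures may also disagree. A participant could walk further with the PMV and report more exertion. The plan does not say what the answer on endurance would then be.

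Timing adds to this. The document carries the line "Study Closeout: June 24, 2024", and its analysis text is in the past tense, so outcome data may have been seen before any rule was fixed. A deciding variable chosen at that point could not be presented as prespecified.

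**Working it through.** **Inputs from the document**
- Named primary measures: 2 (Primary outcomes).
- 6MWT variables accepted: distance and duration (Primary outcomes).
- Alpha: .05 per test, no adjustment (Data Analysis).
- Recruitment goal: 30 participants completing the study (Study Timeline).

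The plan gives no family-wise error rate, power, effect size or standard deviation, so it has no figure of its own to reproduce.

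**Assumptions**
- Any significant result counts. The plan does not say this; it leaves the rule open.
- Tests are two-sided. Sidedness is not stated.
- Each test is itself valid at .05, for example with one paired difference per participant. The Study Timeline says "patients will receive two to six treatment sessions over a three week period", and the plan does not say how these become a pair.
- Correlations between tests are illustrative; the documents give none.

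**Step 1. At least one false difference, either direction**

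For k independent tests the rate is 1 − 0.95^k.
- Two measures: 1 − 0.95² = 0.0975, or 9.75%.
- Two measures, bivariate normal test statistics: 9.1% at correlation 0.5 and 7.8% at 0.8. Negative correlations of the same size give the same values.
- Distance, duration and one Borg score: 1 − 0.95³ = 0.1426, about 14%. At a common correlation of 0.5 it is 12.5%. Distance and duration come from the same walk, so the independence figure is best read as an upper value.

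**Step 2. A false claim that the PMV improves endurance**

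A two-sided .05 test gives a false result in the favourable direction 0.05 / 2 = 2.5% of the time.
- Two independent measures: 1 − 0.975² = 0.0494, or 4.94%.
- Two measures, any correlation: at most 2 × 2.5% = 5%.
- Three independent tests: 1 − 0.975³ = 0.0731, or 7.3%.

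With the two named measures the rate therefore doubles, from 2.5% to about 5%, but does not pass 5%.

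**Step 3. Other success rules**

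If both measures had to be significant, the error would not exceed 5%. If each result supported a claim about its own measure only, each claim would keep its 5%. The plan selects neither rule.

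**Step 4. Power of two remedies**

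Take 30 paired differences and a paired t-test. A standardised difference of 0.53 gives 80% power at .05.
- Distance tested first at the full .05: power for distance stays at 80%.
- Holm on two measures, first step .05 / 2 = .025: power at 0.53 for a measure that must pass alone is 70%. Restoring 80% needs a standardised difference of 0.59.

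**The case against.** The best defence is that the text already points to distance. The Intervention paragraph gives it as the purpose of the walk test, and the description of the Borg scale suggests the post-walk score. The plan claims no family-wise control, and in a small single-hospital study, separate results reported measure by measure at .05 would be an acceptable standard. This stands in part. Those hints make the fix easy and are the reason to choose distance. They are not a designation, because the section that defines the primary outcome puts both measures side by side and adds duration.

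Three stronger readings are tempting, and the documents do not support them.

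- A reader might infer that a false claim of improvement exceeds 5%. For the two named measures tested two-sided it cannot (Step 2). The 9.75% also counts false findings that the PMV makes endurance worse.
- A reader might count four variables and quote 1 − 0.95⁴ = 18.5%. That requires a Borg change score to be tested as well, and the plan says only that scores before and after the walk are collected. It also assumes independence, which is implausible for variables from the same walk or the same scale.
- A reader might infer that the deciding variable was picked after seeing results. The closeout date and past tense make this possible, but nothing in the document shows that it happened.

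**Conclusion.** The concern holds as an unstated decision rule for the primary question. If any significant result counts, the any-difference error for the two named measures is 7.8% to 9.75% over correlations from 0.8 to 0, and at most about 14% with duration added. The false-improvement error for the two measures is at most about 5%, double that of one two-sided test. All these figures depend on the any-significant rule, two-sided tests and a valid single comparison per measure, none of which the plan states.

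The multiplicity is moderate. The larger consequence is interpretive: if distance and Borg-RPE differ, the plan cannot say whether endurance improved. The point should be corrected, but it does not by itself show that any reported result is false.

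**What to change.** In the Primary outcomes and Data Analysis sections:

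1. State that tests are two-sided.
2. Make 6MWT distance the variable that decides the endurance question, at .05.
3. Name one Borg score, post-walk Borg-RPE, and test it at .05 only if distance is significant.
4. Move 6MWT duration to the secondary outcomes.

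This takes about one paragraph. Distance loses no power. The price is that Borg-RPE cannot support a confirmatory claim when distance is not significant.

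An optional alternative is Holm on distance and post-walk Borg-RPE: compare the smaller p-value with .025 and, if it passes, the larger with .05, with each result supporting only its own measure. This costs power (80% to 70% under the assumptions in Step 4) and still does not settle the endurance question when the two disagree.

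If outcome data had been seen before the choice is made, report distance, duration and every Borg score analysed, label the choice of lead variable as post hoc, and do not claim 5% control for it. That adds a short disclosure and needs no new data.
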